**Assessments for Efficacy**

791 The primary outcome of efficacy will be determined by change of HbA1c from baseline  
792 after 26 weeks of treatment. HbA1c will be measured by the clinical laboratory of  
793 Grady Memorial Hospital and Emory University, a NGSP-certified laboratory. Subjects will  
794 complete an 8-point SMBG for at least 1 day before the CGM visits. We will also compare the  
795 time in target range (70-180) as detected by CGM, allowing us to assess glycemic control for > 7  
796 days with frequent testing (CGM and POC BG). We will compare the rate of "responders",  
797 defined as patients HbA1c  
798 <7.0% and no hypoglycemia at week 26.

799  
800

**Assessments for Safety**

801 The safety endpoint of the study will be incidence of hypoglycaemia, as measured by the

802 current standard-of-care of POC monitoring. Subjects will complete an 8-point POC BG log  
803 before weeks -1, 12, 26. In addition, we will perform blinded/professional CGM studies for 7  
804 days, during week -1, 12, and 26. CGM will allow better detection of hypoglycemic events,  
805 particularly asymptomatic and nocturnal hypoglycemia, usually not detected by POC monitoring.  
806 It will also provide critical information on time in glycemic range and glycemic variability. We will  
807 also compare differences in glycemic variability, by SD, %CV and MAGE. GV will be calculated  
808 by mean daily standard deviation (SD) of glucose values in absolute terms, and as a percentage  
809 of variance from the overall mean (%CV). These are measures of dispersion of glucose values  
810 around a measure of central tendency, which represents the overall glucose excursion during  
811 the study. We will also analyze GV by mean amplitude of glycemic excursion (MAGE), which  
812 represents the average of all BG excursions (up or down), with a magnitude of > 1 standard  
813 deviation of all BG measures.

814

815 **Potential Risks to the Subjects:**

816 **Hypoglycemia.** It is possible that following the proposed protocol, subjects receiving IDegLira  
817 or Basal-bolus may develop hypoglycemia, as defined above.

818 **Gastrointestinal side effects**, including nausea and vomiting are more common in patients  
819 treated with liraglutide compared to placebo. The frequency of nausea and vomiting is reported  
820 in up to 5-15% patients receiving IDegLira. The number of adverse events will be collected at  
821 each telephone contact or clinic visit. There have been few reported events of acute  
822 pancreatitis. Subjects should be informed of the characteristic symptoms of acute pancreatitis:  
823 persistent, severe abdominal pain. If pancreatitis is suspected, Degludec-liraglutide should be  
824 discontinued. If the investigator suspects acute pancreatitis, all suspected drugs should be  
825 discontinued until confirmatory test have been conducted and appropriate treatment should be  
826 initiated. Subjects diagnosed with acute pancreatitis (as a minimum 2 of 3: characteristic  
827 abdominal pain, amylase and/or lipase >3xUNR or characteristic findings on CT scan/ MRI  
828 should be withdrawn from the study. In a cardiovascular outcomes trial (LEADER trial) 3.1% of  
829 patients treated with liraglutide, versus 1.9% of placebo treated patients reported an acute  
830 event of gallbladder disease, such as cholelithiasis or cholecystitis. The majority of events  
831 required hospitalization or cholecystectomy. If cholelithiasis is suspected, gallbladder studies  
832 and appropriate clinical follow-up will be indicated.

833

834 **Protection against Risks:**

835 We will follow safeguards to minimize the risk to our subjects: a) we will carefully monitor  
836 response to medical treatment every 1-2 weeks by telephone contact and every 1-2 months

837 during clinic visits, b) women of reproductive age who are sexually active will undergo a urine  
838 pregnancy tests prior to participation in the study and in-person visits as deemed by the  
839 investigator, c) female subjects who are pregnant, breast-feeding, or not willing to use  
840 appropriate contraception at time of enrollment will not be included in the study, d) patients with  
841 significant comorbidities such as chronic kidney disease greater than stage III, liver cirrhosis,  
842 gastroparesis, and pancreatic disorders will be excluded from the study. Hypoglycemia: Patients  
843 will receive diabetes education and will be instructed on hypoglycemia sign/symptoms and  
844 treatment. Patients will be asked to call the diabetes center and/or PCP in the event of  
845 hypoglycemia. If a patient develops hypoglycemia, the dose of basal insulin will be reduced (see  
846 treatment algorithm). Gastrointestinal side effects including nausea and vomiting may be  
847 expected, more commonly in patients treated with liraglutide. In subjects with suspected acute  
848 pancreatitis liraglutide and other potentially suspect medicinal products should be discontinued  
849 until confirmatory tests have been conducted and appropriate treatment initiated.

850

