Trial material																		
Drug dispensing		X				X				X		X						
Drug account			X		X					X		X				x		
End-of-Trial															x			

391 \*+/- 3 days. \*\*+/- 7 days. Labs: ^ pregnancy test, ketones, lipid panel^\* and GAD65 (If concern for Type 1 diabetes, GAD65 and ketones  
392 will be ordered during screening, per PI discretion). Pregnancy test for WOCP as deemed by investigator & fasting defined as at least 8  
393 hours without food or drinks or diabetes medications, except water and other prescribed medications.  +/- 7 days, but before  
394 randomization visit. Fasting glucose could be obtained from a chemistry sample obtained during the visit or POC BG. Body  
395 measurement includes: weight, height and waist and hip circumference. @ During "randomization" and "vital signs" visits, subjects will  
396 receive training on device use.

397 **Treatment of subjects:**

398 **Group 1) IDegLira Group**

399 • Discontinue OADs (SU, DPPIVi, glinides, and pioglitazone), except metformin  
400 (unless contraindicated) and SGLT2i.

401 • Start IDegLira at 16 dose steps (degludec 16 units/liraglutide 0.6 mg), per U.S  
402 labeling indications and/or provider discretion.

403 • IDegLira will be given once daily, at the same time of the day with or without food.

404 • IDegLira will be titrated until the maximum dose (50 steps) is reached, up to target fasting  
405 BG between 70 and 100 mg/dl (Treat-To-Target Trial protocol), see algorithm below.

406 • Titration will occur twice a week: 1) self-titration by patients once a week and 2) phone call/  
407 contact by research team once a week, for the initial 8 weeks. After that, patients will self-  
408 titrate study medications per dosing algorithm.

409 • IDegLira will be titrated by 2-step-dose increment (2 IU of degludec and 0.072 of liraglutide),  
410 to a maximum of 8 steps per week.

411 • The maximum allowed dose of IDegLira 50 dose steps provide 50 U of degludec and 1.8mg  
412 of liraglutide.

413 • Titration will be performed twice weekly (every 3 to 4 days) based on the previous self-  
414 monitored fasting (pre-breakfast) BG measurement (mean of 3 consecutive days). Patients  
415 will be provided with self-titration algorithms for insulin adjustments.

416 • Subjects not at goal (fasting or mean SMBG from 3 consecutive days > 300 mg/dl) requiring  
417 > 50 dose steps of IDegLira, will be considered “treatment failures”. Degludec will be added  

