- 781 • Sensor removal (after 7 days).

782 During each visit, participants will have their insulin dose titrated to achieve a fasting  
783 glucose 70-100 mg/dL as detailed in the insulin titration algorithm. Once the fasting glucose 3-  
784 day average is <100 mg/dL, insulin doses will be kept constant, unless the participant  
785 experiences recurrent or severe hyperglycemia.

786  
787  
788  
789  
790

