**1152           Precautions/Over-dosage**

1153           We will follow safeguards to minimize the risk to our subjects: a) we will carefully monitor  
1154 capillary blood glucose and reported symptoms. To minimize significant clinical events, we will  
1155 exclude patients with history of significant liver, renal or cardiac failure in this study.

1156

1157           Hypoglycemia can occur during the treatment with insulin. Hypoglycemia will be treated  
1158 accordingly to the best local practices, and insulin will be adjusted as per a predefined  
1159 algorithm. Subjects will be instructed to not exceed the maximum dose of IDegLira of 50  
1160 steps. Subjects will be instructed to maintain good hydration, and to report the presence of  
1161 severe nausea, vomiting, or diarrhea. Insulin doses will be adjusted for hypoglycemic values.

1162

1163

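### Read literally, the dose-hold sentence after Visit 18 cancels the titration tables' own reductions for low glucose, and no text ranks the reduce-after-hypoglycaemia rule against the 3-day-mean tables

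*Combined protocol and SAP*

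**What the plan says.** **Rules triggered by an event.** Protection against Risks: "If a patient develops hypoglycemia, the dose of basal insulin will be reduced (see" the treatment algorithm. Precautions/Over-dosage: hypoglycaemia is treated "accordingly to the best local practices, and insulin will be adjusted as per a predefined" algorithm, and the same paragraph ends by saying that doses are to respond to hypoglycaemic values. The section on time-points for the 8-point SMBG profile says that a reading below 70 mg/dL calls for an intervention, and sends the reader to the safety section for it.

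**The algorithm.** In the IDegLira group, titration uses the self-"monitored fasting (pre-breakfast) BG measurement (mean of 3 consecutive days"). The IDegLira/degludec table has no heading on its glucose column, so its 3-day basis comes from that bullet. In the basal-bolus group, the degludec and aspart tables are themselves headed as 3-day means. Both basal tables give -2 below 70 and -4 below 56. Above 45 U/d the cut becomes a percentage: 10% in both rows for IDegLira, and 5% (below 70) or 10% (below 56) for basal-bolus degludec.

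**The hold.** The paragraph closing the Visit 18 text says that at each visit doses are titrated to a fasting "glucose 70-100 mg/dL as detailed in the insulin titration algorithm. Once the fasting glucose 3"-"day average is <100 mg/dL, insulin doses will be kept constant, unless the participant" "experiences recurrent or severe hyperglycemia".

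**Who titrates.** In both arms, patients make one of the two weekly adjustments and the other follows "contact by research team once a week, for the initial 8 weeks. After that, patients will self"-titrate by the dosing algorithm.

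**The concern.** There are two separate faults.

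First, the hold has no lower limit. A mean of 67 or 55 is below 100, so the sentence keeps the dose where the tables cut it. Its only exception is for high glucose, which is the wrong direction for a patient already below target.

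Second, the cross-references do not arrive at a dose. The SMBG section points to the safety section, the safety section points to the algorithm, and the algorithm has no step for an event. It averages a low reading with two others and can return no change or an increase, although the safety text says that basal insulin is reduced.

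Patient safety is at stake, in a trial that titrates to fasting 70-100 mg/dL and names hypoglycaemia as its safety endpoint.

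**Working it through.** The plan states no figure on this point, so the check reads its rules against one another. The glucose triplets are illustrations chosen here, not trial data.

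**1. Hold against table.** Inputs: the basal table rows and the hold sentence.

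| Fasting values | Mean | Table | Hold, read literally |
|---|---|---|---|
| 65, 68, 69 | 202/3 = 67.3 | -2 | no change |
| 50, 55, 60 | 165/3 = 55.0 | -4 | no change |

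The two texts give different doses for the same patient.

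**2. One low fasting reading against table.** Let r be the low reading and m the average of the other two, so the 3-day mean is (r + 2m)/3.

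- Mean below 70 (reduce) when m < (210 - r)/2.
- Mean 71 to 100 (no adjustment) when m runs from (213 - r)/2 to (300 - r)/2.
- Mean 101 or more (increase) when m ≥ (303 - r)/2.

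| r | Reduce if m is below | No adjustment if m is | Increase if m is at least |
|---|---|---|---|
| 45 | 82.5 | 84 to 127.5 | 129 |
| 53 | 78.5 | 80 to 123.5 | 125 |
| 69 | 70.5 | 72 to 115.5 | 117 |

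The small gaps between columns are means that fall between the printed rows. Two examples:

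- 45, 110, 110: mean 265/3 = 88.3, row 71-100, no adjustment.
- 45, 150, 150: mean 345/3 = 115, row 101-120, +2.

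Protection against Risks calls for a basal reduction in both.

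**3. Lows that are not fasting.** Only fasting values drive IDegLira and degludec. A low before a later meal or at bedtime can enter the aspart mean in the basal-bolus arm, but no table in the IDegLira arm. The 3-4 am profile reading enters no table in either arm.

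**4. Limit in the IDegLira arm.** "The maximum allowed dose of IDegLira 50 dose steps provide 50 U of degludec and 1.8mg" of liraglutide, so an increase is possible only below 50 steps. At the cap the table can still hold where the safety text says reduce. Basal-bolus degludec has no maximum, so both outcomes can occur there.

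**5. Contact after week 8.** Table 1 schedules weeks 10, 12, 14, 16, 20, 24 and 26, which are gaps of 2 to 4 weeks. Protection against Risks describes telephone contact every 1-2 weeks. On either account, patients adjust doses themselves between contacts.

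**The case against.** The strongest reply is that the documents already intend action on individual lows. Three places say so: the SMBG section, Protection against Risks and Precautions/Over-dosage. They can be read together, with the safety text supplying the trigger and the table supplying the step. The IDegLira table has no heading tying its low rows to a mean. A study physician advises at every contact, the follow-up visit sections allow doses to be adjusted as needed in both arms, aspart and rescue degludec changes are at provider discretion, and patients are asked to call after an event. The hold is worded for visits, follows a sentence naming the 70-100 target, and its exception looks like a typing slip.

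Most of this stands, and it limits the point. It does not remove it. No sentence gives the event rule precedence or says which row to use after a single event. The degludec and aspart tables are explicitly headed as means. A slip in an operative dosing sentence still needs correcting, and the documents do not confirm that it is one.

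A reader might infer that the protocol tells patients to ignore lows, or that patients will come to harm. The documents do not support this. No text says to ignore a low, and that route to harm depends on what the patient titration sheet says, which the documents do not include. A reader might also infer a bias in the hypoglycaemia or HbA1c comparison. Nothing in the documents shows how often these patterns would arise or that they would differ between arms.

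**Conclusion.** The concern holds as a conflict between dosing rules. The hold, read literally, contradicts the below-70 and below-56 rows. Separately, the 3-day-mean tables can hold or raise a dose after a low for which the safety text calls for a reduction, and nothing expressly ranks the two.

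The size is what the rules permit: with one fasting reading of 45, the table gives no reduction once the other two average 84 or more, and an increase once they average 129 or more. This assumes that the tables are applied as written, on 3-day means, without physician intervention. It is not an estimate of how often this would happen. The existing safeguards reduce the risk, but none is stated to override the tables. It is worth correcting because the text concerns dosing and the change is small.

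**What to change.** **In the paragraph after Visit 18:** limit the hold to a 3-day fasting mean of 71-100 mg/dL and make its exception cover hypoglycaemia.

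**In the titration algorithms of both arms, add one sentence:** after hypoglycaemia since the last titration (any SMBG below 70 mg/dL, or a severe episode), no dose is increased and the reduction in Protection against Risks applies, using that arm's existing below-70 or below-56 row, whatever the 3-day mean, unless the study physician decides otherwise. In patients on rescue therapy, apply the cut to the rescue degludec, since the protocol keeps their IDegLira dose fixed.

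**In the patient titration sheet:** carry the same sentence over if it is not already there.

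**Cost:** a few sentences, possibly a revised sheet with brief training, and slightly slower titration after isolated or falsely low readings. The existing difference between arms would also be used somewhat more often. For a reading of 56-69 at a dose of 50, the cut is 10% × 50 = 5 steps for IDegLira and 5% × 50 = 2.5 units for basal-bolus degludec. The sponsor should confirm that this difference is intended.

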418 to IDegLira as “rescue” basal insulin therapy. The dose of IDegLira will remain unchanged.

419 • The dose of “rescue” Degludec will be recorded and titrated twice weekly to target FPG of  
420 70-100 mg/dl, per provider discretion, as shown below.

Titration algorithm for IDegLira and Degludec pens	Insulin dosage IU/d)*
$\geq 181$	8
141-180	6
121-140	4
101-120	2
71-100	no adjustments
$<70$	-2 If dose $> 45$ U/d, decrease by 10%
$<56$	-4 If dose $> 45$ U/d, decrease by 10%

\* Maximum titration dose per week: 8 units

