632 who do not meet all the inclusion criteria at Visit 1 will be considered screen failures and will not  
633 be randomized to participate in the study.

634  
635 During this visit, the investigator will insert the CGM to obtain baseline information  
636 (before drug exposure). During this visit, patients will receive training on CGM use and reinforce  
637 SMBG diary collection. Trained personnel will proceed with sensor insertion. After that, the  
638 sensor will be activated, the CGM session will be started.

639  
640 Eligible patients will be trained on the use of the glucose meter to monitor their BG levels  
641 (i.e. 8-point SMBG). Patients will be given diabetes diaries and associated training to record all  
642 glucose levels, insulin doses, and episodes of hypoglycemia. Subcutaneous injections  
643 administration technique will be reviewed prior to randomization to ensure good technique.  
644 Reinforcement will be provided as needed during the follow-up visits.

645  
646 Patients will be instructed in performing glucose testing at home before meals, with a  
647 minimum of 2 out of the 4 pre-meal and/or bedtime glucose measurements per day. In addition,  
648 patients must perform an 8-point SMBG for at least 1 day prior to week 0, 12, 26, as follows:

649  
650  
651 **Time-points for 8-point SMBG profile:**  
652

653 The blood glucose levels should be measured and recorded in the diary (including date,  
654 actual clock time and blood glucose value) at the following time points, always starting with

655 measurement before breakfast. Subjects will be instructed to collect the SMBG on a day where  
656 the subject does not anticipate unusual strenuous exercise.

657 • Before breakfast  
658 • 90 min after the start of breakfast  
659 • Before lunch  
660 • 90 min after the start of lunch  
661 • Before dinner  
662 • 90 min after the start of dinner  
663 • At bedtime  
664 • In the middle of the night at 3 or 4 am

665 Subject will also be instructed to check and record BG when hypoglycemia is suspected. Values  
666 < 70 mg/dl should trigger an intervention, as described below (safety section).

667

668 Instructions for Run-In Period (2 weeks):

669 The main purpose of this period is to ensure that patients can comply with 8-point SMBG, pen  
670 instructions and trial recommendations.

- 671 • Oral antidiabetic agents will be continued at same dose until randomization visit.  

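### Basal insulin is to be cut after hypoglycaemia, but the algorithm cited for the cut reads only the 3-day fasting mean and can hold or raise the dose after a low

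*Combined protocol and SAP*

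**What the plan says.** **The safeguard.** Protection against Risks: "If a patient develops hypoglycemia, the dose of basal insulin will be reduced (see" the treatment algorithm). The statement is unconditional and gives no size for the cut.

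**Related statements.** Under Time-points for 8-point SMBG profile, a meter value below 70 mg/dL "should trigger an intervention, as described below (safety section"). Precautions/Over-dosage says "Insulin doses will be adjusted for hypoglycemic values". The Definitions section identifies documented symptomatic hypoglycaemia from an SMBG or CGM value at any time of day, so it is neither a mean nor restricted to fasting. The 8-point profile includes a night reading: "In the middle of the night at 3 or 4 am".

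**The algorithm.** In the IDegLira arm, titration uses the self-"monitored fasting (pre-breakfast) BG measurement (mean of 3 consecutive days"). The Basal-Bolus Insulin Group section has the same rule, and the header of its degludec table repeats that the rows are read on the 3-day fasting mean. In both tables a value of 71-100 gives no change, 101-120 gives +2, below 70 gives -2 and below 56 gives -4. Above 45 U/d the below-70 row becomes a percentage cut: 10% in the table for IDegLira and degludec pens, 5% in the basal-bolus degludec table.

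**Who applies it.** The research team makes weekly contact "for the initial 8 weeks. After that, patients will self"-titrate. In the IDegLira arm patients "will be provided with self-titration algorithms for insulin adjustments"; the basal-bolus arm is also self-titrated by algorithm after week 8.

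**The holding rule.** The paragraph that closes the Visit 18 section keeps doses constant once the 3-day fasting average is below 100 mg/dL. Its only exception is recurrent or severe hyperglycaemia.

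**The concern.** The safety section points to a rule that does not take the event as an input. A low enters the basal algorithm only if it is a pre-breakfast reading, and then only as one third of a mean. A low at night, before lunch or at bedtime does not enter at all.

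Two things are at stake. The first is patient safety in a treat-to-target design aiming at fasting glucose of 70-100 mg/dL, where patients work from the algorithm without weekly support after week 8. The second is the comparison in Specific Aim 2, where hypoglycaemia is a superiority outcome. The dose response to a low, and so the chance of a repeat event, depends on which section is followed, and the tables differ by arm. Basal-bolus has a partial route for pre-meal and bedtime lows through the aspart table, again on a 3-day mean. IDegLira has no input other than fasting glucose.

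**Working it through.** The plan gives no figure for this point, so there is none to reproduce. The check applies the tables to readings that contain a low.

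**1. Fasting low averaged out.** Fasting 58, 105, 107: (58 + 105 + 107)/3 = 90. Row 71-100: no change. The holding rule also applies, since 90 is below 100. Protection against Risks requires a reduction.

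**2. Night low.** 52 mg/dL at 3 am with symptoms; fasting 104, 108, 112: (104 + 108 + 112)/3 = 108. Row 101-120: +2. Protection against Risks requires a reduction.

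**3. When does a fasting low reach a cut row?** With one reading x, the mean is below 70 only if the other two average less than (210 - x)/2. The mean reaches 101, and the dose rises, if they average at least (303 - x)/2.

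| Low x (mg/dL) | Others must average below, for a cut | Others average at or above, for an increase |
|---|---|---|
| 69 | 70.5 | 117 |
| 54 | 78 | 124.5 |
| 40 | 85 | 131.5 |

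For example, 50, 130, 140 averages 106.7 and gives +2.

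**4. Non-fasting low.** It does not enter the basal table, so by itself it never produces a basal cut. No assumption is needed here.

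**5. Contact gaps.** Table 1 has contacts at weeks 8, 10, 12, 14, 16, 20, 24 and 26, so the 4-week gaps are weeks 16-20 and 20-24. If twice-weekly titration continues, each gap holds 4 x 2 = 8 titrations. At a fasting mean that stays at 101-120, the table adds 8 x 2 = 16 units (IDegLira stops at 50 steps). This is a ceiling: it needs the mean to stay in that row and nobody to intervene.

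**6. Illustration of averaging.** The documents give no day-to-day SD. Assume independent normal fasting readings with mean 85 mg/dL, the midpoint of the target. P(any of 3 below 70) = 1 - (1 - Φ((70 - 85)/SD))³ and P(mean below 70) = Φ((70 - 85)/(SD/√3)). A mean below 70 implies at least one reading below 70, so the share of windows with a low that miss a cut row is 1 - P(mean)/P(any).

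| SD | P(any < 70) | P(mean < 70) | Share missing a cut row |
|---|---|---|---|
| 10 | 0.187 | 0.005 | 97.5% |
| 15 | 0.404 | 0.042 | 90% |
| 20 | 0.537 | 0.097 | 82% |
| 25 | 0.618 | 0.149 | 76% |

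Over assumed means of 85-110 and SDs of 15-30, windows containing a fasting low led to a cut in about 0-29%, no change in about 65-97% and an increase in about 0-31%.

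**7. Percentage rows.** At 50 U/d in the below-70 row: 0.10 x 50 = 5 units or steps in the first table, 0.05 x 50 = 2.5 units in the second. The first table is titled for degludec as well, so degludec has two rules and no reason is given.

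**The case against.** The best defence is that the sections can be read together: Protection against Risks supplies the trigger, and the -2 and -4 rows supply the size. The table in the IDegLira section shows no glucose header in the text available, so the mean there comes only from the titration bullet. This reading is sensible and is what the fix writes out. It is not what the algorithm says, though: the bullets in both arms and the basal-bolus header specify the mean.

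The second defence is that other safeguards exist. Patients are taught to recognise and treat lows and are asked to call, a study physician advises at each contact, doses may be adjusted as needed, and the 4-week gaps are only two stretches of the schedule. All of this stands and lowers the risk. None of it sets a trigger or a size, or tells the self-titrating patient to hold.

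The holding rule should not be over-read. Taken literally it would forbid the tables' own cuts below 70, so it is probably a slip rather than a deliberate bar. It still needs correcting.

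Several stronger readings are tempting, and the documents do not support them:

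- *Three sections each promise a basal cut.* Only Protection against Risks does. The 8-point SMBG text says intervention, which could mean treating the low. Precautions/Over-dosage says adjusted and names neither basal insulin nor a reduction.
- *The patients' instruction sheet lacks a stop rule.* The sheet is not in the documents.
- *A pre-meal low can never lead to a cut in IDegLira.* The pre-breakfast reading is that arm's input and can, if the mean falls below 70.
- *The 44% of an earlier high-HbA1c cohort with a reading below 70 (0.44 x 75 = 33 basal-bolus patients), or the 76-97.5% above, measures lows left without a cut.* The first counts patients with any low; the second rests on an assumed mean and SD. Both are illustrative only.

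**Conclusion.** The point holds: a stated dosing rule can give the opposite of a stated safeguard. The two worked examples and the exclusion of non-fasting lows from the basal table need only the protocol's text. How often this would happen cannot be established from the documents, because the fasting means, the day-to-day SD and the content of the patient sheet are not given.

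This goes beyond missing detail because patients apply the rule themselves after week 8 and hypoglycaemia is a comparative outcome. A reader might infer that it threatens the HbA1c comparison. Nothing here supports that, and no effect on power or on the non-inferiority conclusion is claimed. The change should be made, but the primary analysis does not depend on it.

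**What to change.** Keep the 3-day mean for increases. In both arms' tables and self-titration instructions, add that any SMBG value below 70 mg/dL, or any symptomatic or severe event, since the last titration means no increase, and that the existing below-70 (-2) and below-56 (-4) rows apply to that single value. State which row applies when an event has no meter reading. In basal-bolus, a daytime low after a meal dose cuts the preceding aspart dose and a fasting or nocturnal low cuts basal; word Protection against Risks to match. Name hypoglycaemia as an exception in the holding rule. Use one percentage in the below-70 row above 45 U/d, or explain the difference. If the sponsor prefers the mean rule throughout, Protection against Risks should stop promising a reduction after every low.

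These are text edits with no new visits or tests, but they have a clinical cost: more dose cuts and somewhat higher fasting glucose. If basal-bolus has more lows, as Aim 2 expects, its insulin would be cut more often, which could slightly favour IDegLira on HbA1c. Having the same rule in both arms does not remove that asymmetry. It is acceptable because Protection against Risks already commits the trial to reductions after hypoglycaemia.
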